1. INTRODUCTION

This Statistical Analysis Plan (SAP) outlines the statistical methods for the display, summary and analysis of data collected within the scope of Theracos Sub, LLC protocol version 3.0 dated 21-Aug-2018. As with any SAP, the proposed methods and approaches to the data analysis should be deemed as flexible. The analysis of the data should allow changes in the plan to the extent that deviations from the original plan would provide a more reliable and valid analysis of the data. As such, the statistical analysis to a certain degree is iterative since much of the planning is based on assumptions that require verification. The purpose of this plan is to provide general guidelines from which the analysis will proceed. Nevertheless, deviations from these guidelines must be substantiated by a sound statistical rationale.

This SAP should be read in conjunction with the study protocol and the Case Report Forms (CRFs). This version of the SAP has been developed using the latest version of the protocol mentioned above and the final version of the annotated CRFs dated 11-SEP-2018.

This document details the analysis of the data collected in the study and the presentation of the results of the analyses. The table, listing, and figure (TLF) shells are displayed in a companion document which provides information on the layout of the data displays.

All statistical analyses will be performed using SAS[®] version 9.4. Adverse events will be coded using the latest version of the Medical Dictionary for Regulatory Activities (MedDRA version 21.0 or newer). Concomitant medications will be coded using the World Health Organization Drug Dictionary (WHO-DD).

This is a phase 1, open-label, parallel-group study designed to evaluate the effect of moderate hepatic impairment on the pharmacokinetics (PK) and pharmacodynamics (PD) of orally administered bexagliflozin tablets, 20 mg.

Approximately 16 subjects (eight with moderate hepatic impairment [Child-Pugh total score 7-9] and eight healthy, matched controls) will receive a single oral dose of bexagliflozin tablet, 20 mg.

The Child-Pugh grading system will be used to assess the severity and prognosis of hepatic disease. The study population will be comprised of male and female subjects with hepatic impairment conforming to the Child-Pugh classification of B (Child-Pugh total score 7-9) based on the Child-Pugh scoring method described in Appendix 3.

For each enrolled subject with liver dysfunction a matched control subject (healthy subject) of similar age (± 10 years), weight ($\pm 10\%$), sex, and smoking status will be enrolled.

Blood samples to characterize the PK profile of bexagliflozin will be collected at pre-dose and at 0.5, 1, 2, 3, 4, 5, 6, 8, 10, 12, 16, 24, 36, and 48 hrs post-dose.

Urine samples for PD analysis will be collected at pre-dose (-12 to 0 hr), and in the following intervals post-dose 0–12, 12–24, 24–36, and 36–48 hrs.

Plasma concentrations of bexagliflozin will be determined by a validated liquid chromatography-mass spectrometry (LC-MS/MS) assay.

The unbound fraction of bexagliflozin will be determined at the maximal plasma concentration and at 24 h (or earlier if the 24 h post-dose sample has a concentration below the limit of quantitation) postdose for each subject by an equilibrium dialysis method.

(See Protocol Sections 3.1 to 3.3 for additional details).

2. STUDY OBJECTIVES

2.1 Primary Objective

To evaluate the effect of moderate hepatic impairment on the PK and PD of a single oral dose of bexagliflozin tablets, 20 mg.

2.2 Secondary Objectives

To assess the safety and tolerability of bexagliflozin in subjects with moderate hepatic impairment.

3. STUDY DESIGN

3.1 Study Design

This is a phase 1, open-label, parallel-group study. Subjects will be screened within 28 days of the initiation of study drug dosing. Eligible subjects who consent to participate in the study will receive a single oral dose of bexagliflozin tablets, 20 mg, and then will be kept under close medical surveillance at the trial center for at least 48 hrs following drug administration. Subjects will return for an end-of-study examination within 13 days of the last PK sample collection.

Blood samples for characterization of the PK profile of bexagliflozin will be collected at pre-dose and at 0.5, 1, 2, 3, 4, 5, 6, 8, 10, 12, 16, 24, 36, and 48 hrs after oral administration of bexagliflozin.

Urine samples for PD analysis will be collected prior to dosing (-12 to 0 h) and in the following intervals after dosing: 0–12, 12–24, 24–36, and 36–48 hrs.

Plasma concentrations of bexagliflozin will be determined by a validated liquid chromatography-mass spectrometry (LC-MS/MS) assay.

The unbound fraction of bexagliflozin will be determined at 24 h postdose and maximal plasma concentration for each subject by equilibrium dialysis.

3.2 Randomization

Approximately 16 subjects (eight with moderate hepatic impairment [Child-Pugh total score 7-9] and eight healthy, matched controls) will be enrolled. This study is non-randomized.

3.3 Hypothesis Testing

No formal statistical hypothesis testing will be conducted for this study.

3.4 Interim Analysis

There will be no interim analysis conducted.

3.5 Sample Size

The sample size for this study is not based upon formal statistical consideration. The sample size is considered adequate to detect clinically relevant PK differences between healthy and hepatic impairment subjects.

3.6 Schedule of Assessments and Study Procedures

|

Table 1. Schedule of Events

Study activity	Screening		In-Clinic				Follow-up D15 ± 1 day
	D -28 to -1	D0	D1 pre-dose	D1 post-dose	D2	D3	
Medical history and ICF	X						
Screening for I/E criteria	X	X					
Physical exam ¹	X	X	X				X
Demographics	X						
Admission and discharge		X				X	X
Vital signs ²	X		X	X	X	X	X
ECG ³	X		X	X		X	X
Urinalysis ⁴	X	X	X			X	X
Blood draw for clinical lab tests ⁵	X	X	X			X	X
Blood sample for PK ⁶			X	X	X	X	
Urine collection ⁷		X	X	X	X	X	
Urine pregnancy test (Female only)	X	X					X
Adverse event and concomitant medication		X	X	X	X	X	X
Study termination ⁸							X

Abbreviations: D = day; ECG = electrocardiogram; ICF = informed consent form; I/E = inclusion/exclusion; PD = pharmacodynamic; PK = pharmacokinetic.

1. Weight and height will be recorded as part of the physical examination. Height will be recorded once at screening only. A complete physical exam (PE) will be performed at screening and on clinical admission (D0). A partial PE will be performed on day 1 and at the follow-up visit.
2. Vital signs include: pulse, body temperature, respiratory rate, systolic and diastolic blood pressure. Vital signs will be determined at predose and at 4 h, 24 h (day 2), 48 h (day 3) postdose and at the follow up visit.
3. 12-lead ECG will be conducted after 5 mins of resting. ECG data will be recorded at screening, on day 1 at predose and at 4 h postdose and day 3, and at the follow up visit and when clinically indicated.
4. A clean sample will be collected at each visit. If urine dipstick is positive for protein, leukocyte esterase, blood or nitrites, a microscopic examination will be performed. If the microscopic exam is suggestive, a culture may be performed at the investigators discretion. Urine drug screen will be performed at the screening visit and clinic admission (D0). Alcohol (via urine or breath) will be tested at clinic admission (D0) only.
5. Blood sample at the designated visits for clinical chemistry and hematology parameters are listed in [Table 1](#). Infectious disease testing will be conducted at screening only.
6. Plasma samples for the PK profile of bexagliflozin will be collected at pre-dose and at 0.5, 1, 2, 3, 4, 5, 6, 8, 10, 12, 16, 24, 36, and 48 h post-dose.
7. Urine for PD will be collected at pre-dose (h -12 to 0), and during the following intervals post-dose 0-12, 12-24, 24-36, and 36-48 h.
8. If early withdrawal occurs, activities scheduled for the follow up visit should be conducted. Reasons for all withdrawals should be recorded on the CRF.

4. DATA AND ANALYTICAL QUALITY ASSURANCE

The overall quality assurance (QA) procedures for the study data, statistical programming and analyses are described in Everest's Standard Operating Procedures (SOPs). Detailed data management (DM) procedures are documented in the Data Management Plan (DMP), Data Validation Check Specifications, and Data Review Plan. Detailed statistical and programming quality control (QC) and QA procedures are documented in the Statistical Analysis and Programming QC/QA Plan.

The study endpoints and analytic approaches are both prospectively defined and documented in the protocol and in this SAP. The SAP will be finalized, and protocol violations will be identified and decisions for inclusion and exclusion of subjects from the PK and PD Populations will be made prior to the database lock and data analysis.

5. ANALYSIS POPULATIONS

Three subject populations will be evaluated during this study and are defined as follows:

5.1 Safety Population

The Safety Population will include all subjects who have been dispensed study drug and who have received study drug. Subjects will be analyzed according to the respective hepatic function group.

5.2 Pharmacokinetic Population

The PK Population will include all subjects who have been dispensed study drug and who have received study drug and provided an observation for ≥ 1 primary PK endpoints, and without major protocol violations. The PK Population will be used to summarize the PK parameters.

5.3 Pharmacodynamic Population

The PD Population will include all subjects without major protocol violations who have been dispensed study drug and who have received study drug and who have had pre-dose urine collection and at least a postdose 0-12 hr urine sample collected. The PD Population will be used to summarize the PD parameters.

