6.6.2.3 Urine Collection for PD

Predose urine samples must be collected from -12 to 0 h for baseline measurement. Subjects will empty their bladders prior to dosing. Postdose urine will be collected without preservative in four (4) batches at 0-12, 12 to 24, 24 to 36, and 36 to 48 h after oral administration of bexagliflozin. Urine must be refrigerated at 2-8 °C during collection. After collection, the total volume of each batch and collection time will be recorded. A 20 mL aliquots of the urine at each batch will be prepared from well-mixed urine collections. One aliquot of the urine samples will be analyzed for urinary glucose and creatinine at the local lab (for PD analysis).

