9.3.3 PD Population

The PD Population will include all subjects without major protocol violations who are dispensed study drug and who produce at least the first 12 h postdose urine. The PD Population will be used to summarize the PD parameters.

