9.6 Pharmacodynamic Analysis

The PD parameters, glucose concentrations, creatinine concentrations, UGE and UGE normalized by urinary creatinine, including UGE_{t1-t2} over specified time interval, and total 24-hour, 48-hour UGE, will be determined. UGE_{t1-t2} (mg) will be derived from urine volume (V_{t1-t2} , mL) \times glucose concentration ($mg\ dL^{-1}$) / 100. UGE and nUGE will be listed and summarized by hepatic function group using descriptive statistics.

Reported predose values for PD data that are below the defined limit will be set to zero. Any missing values or values below the reported defined limit that appear after predose for PD data will be set to missing.

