7.3 Pharmacodynamic Analyses

Urinary glucose excretion (UGE) and creatinine normalized UGE (nUGE) will be determined as PD parameters at baseline and up to 48 hours post-dose.

UGE_{t1-t2} (g) will be derived from urine volume and glucose concentration as follows:

[urine volume (V_{t1-t2} , mL) x glucose concentration (mg/dL)/100]/1000.

UGE normalized by urinary creatinine will be calculated as per below:

[urine volume (V_{t1-t2} , mL) x creatinine concentration (mg/dL)/100]/1000.

The total 24-hour and 48-hour quantity of glucose excreted in urine will be calculated by adding the amounts collected during each post-dose interval.

Descriptive statistics will be used to describe any differences in these PD parameters between treatment groups (normal hepatic function and moderate hepatic impairment).

For PD data, reported pre-dose values that are below the defined limit will be set to zero. Any missing values or values below the reported defined limit that appear after pre-dose for PD data (glucose, UGE, creatinine) will be set to missing. Because zero values cannot be included in calculation of a geometric mean, then geometric means and percent CV calculated for data including values below the defined limit will be based only on the subjects without such zero value data

PD data will also be reported in listings.

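### SAP 5.3 adds an undeclared predose-urine condition to the PD Population, and SAP 7.3 has no rule for a 24-h or 48-h UGE total when a batch is missing

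*SAP*

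**What the plan says.** Protocol 9.3.3 defines the PD Population as subjects without major protocol violations "who are dispensed study drug and who produce at least the first 12 h postdose urine". SAP 5.3 keeps the exclusion for major violations but requires subjects "who have had pre-dose urine collection and at least a postdose 0-12 hr urine sample collected". SAP section 10, the place for changes from the protocol, does not mention the added condition, and no reason is given for it elsewhere. Neither definition asks for any urine after 12 h.

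The predose batch has a stated purpose. Protocol 6.6.2.3 says: "Predose urine samples must be collected from -12 to 0 h for baseline measurement". SAP 7.3 says that UGE and creatinine-normalised UGE "will be determined as PD parameters at baseline and up to 48 hours post-dose".

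Protocol 9.6 lists interval UGE and says that "total 24-hour, 48-hour UGE, will be determined". On the derivation, SAP 7.3 says: "The total 24-hour and 48-hour quantity of glucose excreted in urine will be calculated by adding the amounts collected during each post-dose interval". The same section sets post-dose PD values that are missing or below the limit to missing, and SAP 8.1 leaves missing data missing unless another rule applies. No sentence covers a total with one interval missing.

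**The concern.** The collections required for entry to the population do not match those that the endpoints need, in two ways.

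- **Entry is stricter than the protocol where the post-dose endpoints do not need it.** Neither document defines a baseline-subtracted or change-from-baseline UGE. A subject with a full 0-48 h collection and a lost overnight batch still falls out of every PD table, because SAP 5.3 applies to the whole population and not to the baseline output alone.
- **The totals have no completeness rule.** A subject with urine for 0-12 h only is in the population used to summarise 24-h and 48-h UGE. Two programmers could follow the SAP and differ: in SAS, the SUM function skips missing values, while the plus operator returns missing. The first would put a 12-hour amount under a 24-hour or 48-hour label.

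PD shares the primary objective with PK, and there are about eight subjects per group, so one subject's handling can show in a group summary. The case is foreseeable. Protocol 6.9 allows withdrawal at any time, protocol 7.7 excuses subjects terminated after dosing from further PD samples, and protocol 5.4 does not replace safety withdrawals.

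**Working it through.** The plan states no figure to reproduce. The sample size has no formal statistical basis (protocol 9.2, SAP 3.5), and PD is described without a test or confidence interval. The sizes below are for scale.

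**Inputs.** n = 8 per group (protocol 3.1, SAP 3.2). Batches are predose (-12 to 0 h), 0-12, 12-24, 24-36 and 36-48 h (protocol 6.6.2.3). The documents do not give the share *s* of a subject's true total that falls in 0-12 h. It is assumed to be 0.50-0.75 of the 24-h total and 0.25-0.60 of the 48-h total; 0.50 and 0.25 correspond to equal intervals.

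**Step 1: which output uses which batch.**

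| Output | Batches used | Predose needed? |
|---|---|---|
| Baseline UGE, nUGE | predose | yes |
| Interval UGE, nUGE | that interval | no |
| 24-h UGE | 0-12, 12-24 h | no |
| 48-h UGE | all four post-dose | no |

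SAP 5.3 requires predose and 0-12 h for every row.

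**Step 2: cost of one exclusion for a missing predose batch.**

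- Share of the group lost: 1/8 = 12.5%.
- SE of that group's mean: √(8/7) = 1.069, so about 7% larger.
- Between groups, the 90% interval half-width in SD units is t(0.95, n₁+n₂−2) × √(1/n₁+1/n₂). For 8 v 8 it is 0.881; for 7 v 8 it is 0.917. The ratio is 1.041, so about 4% wider.

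**Step 3: effect on a total if available batches are summed.** Suppose one of 8 subjects has only the 0-12 h batch and true totals are equal across subjects. The arithmetic mean shifts by −(1−s)/8. The geometric mean, which SAP 7.3 also mentions for PD, shifts by s^(1/8) − 1.

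| Total | s | Arithmetic mean | Geometric mean |
|---|---|---|---|
| 24-h | 0.50 | −6.2% | −8.3% |
| 24-h | 0.60 | −5.0% | −6.2% |
| 24-h | 0.75 | −3.1% | −3.5% |
| 48-h | 0.25 | −9.4% | −15.9% |
| 48-h | 0.40 | −7.5% | −10.8% |
| 48-h | 0.60 | −5.0% | −6.2% |

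**Step 4: if the total is instead set to missing.** The Step 3 shift does not arise. The n for that total falls by one and the interval summaries are unaffected.

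**The case against.** Five arguments can be made for the plan.

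1. **The predose batch is used.** Baseline UGE and nUGE are named PD parameters, so requiring a baseline in a population that reports baseline is a defensible choice. This stands against any claim that the batch serves no endpoint. It does not explain why a subject without it should also leave the post-dose summaries, nor why the SAP departs from the protocol without saying so.
2. **Missing the batch is already a deviation.** The protocol makes the collection mandatory, so the subject might be excluded under protocol 9.3.3 as well. That depends on the deviation being classed as major, which neither document defines. The SAP makes the exclusion automatic.
3. **The totals may already be safe.** A reader might infer that the SAP sums whatever was collected. The text does not go that far. The phrase "calculated by adding the amounts collected during each post-dose interval" can be read as requiring every interval, and together with the set-to-missing rule and SAP 8.1 it could equally give a missing total. This stands: the gap is an unstated rule, and the bias is conditional on one reading of it.
4. **The 0-12 h minimum is not an error.** The protocol has the same minimum, and such subjects contribute properly to the interval summaries. This also stands.
5. **Few batches should be lost.** Subjects stay in clinic for at least 48 h after dosing, and PD is descriptive and listed by subject, so an incomplete collection would be visible. This limits the likely impact. A reader might also infer that batches would be lost more often in the impaired group and so mimic a hepatic effect; nothing in the documents supports that.

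**Conclusion.** The mismatch between SAP 5.3 and protocol 9.3.3 is established from the text. Followed as written, the SAP drops a subject whose post-dose collection is complete, at a cost of about 7% in the SE of that group's mean and about 4% in between-group precision for each subject lost.

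The second part is an ambiguity and not a demonstrated error. If available batches were summed, one subject of 8 with only 0-12 h urine would lower the arithmetic mean by about 3-6% for the 24-h total and 5-9% for the 48-h total. Those ranges rest on assumed interval shares and equal true totals. If a missing interval makes the total missing, there is no such shift.

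In-clinic collection and a descriptive PD analysis keep the expected impact modest, but both rules are best settled before database lock, when SAP section 4 has the populations decided.

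**What to change.** **SAP 5.3.** Restore the protocol 9.3.3 definition, and require the predose batch only for outputs that report baseline. If the sponsor prefers to keep the predose condition, declare it with its reason in SAP section 10.

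**SAP 7.3.** State that 24-h UGE is computed only when both the 0-12 h and 12-24 h amounts are available, and 48-h UGE only when all four are. Otherwise the total is missing, and the available intervals are still summarised. SAP 7.2 already works at parameter level for PK, where an AUC to infinity with more than 20% extrapolated is listed but left out of summary tables.

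**Below-limit batches.** State separately how a batch that was collected but reads below the limit enters a total. SAP 7.3 sets that value to missing too, so without its own rule it would be treated like a batch that was never collected.

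**Cost.** A few SAP sentences and no new data. The downside is that n may differ between the baseline, interval and total summaries, so each table should show its own n.

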6. SPECIFICATION OF ENDPOINTS AND VARIABLES

6.1 Demographic and Baseline Characteristics

Demographic variables consist of the following:

- Age in years (continuous) derived as the integer value of $(\text{informed consent date} - \text{date of birth} + 1)/365.25$
- Sex
- Race
- Ethnicity

Baseline characteristics consist of the following:

- Body mass index (BMI) (kg m^{-2})
- Weight (kg)

- Smoking status (non-smoker, current smoker, former smoker)
- Height (cm)
- Vital signs (VS)
 - systolic blood pressure (SBP, mmHg)
 - diastolic blood pressure (DBP, mmHg)
 - oral cavity temperature (°C)
 - pulse (beats per minute)
 - respiration rate (breaths/min)
- Electrocardiogram (ECG) parameters
 - RR interval (msec)
 - PR interval (msec)
 - QRS duration/interval (msec)
 - QT interval (msec)
 - QTcB interval (msec) (corrected by Bazett’s formula)
- Medical history and baseline conditions
- Clinical laboratory test values
- Prior and concomitant medication
- Physical examination (PE)

6.1.1 Study Day and Visit Window Definitions

Table 4. Time Windows for Safety Assessments

Time Windows for Safety Assessments			
Scheduled Visit Number	Visit (label)	Time Interval (day)	Nominal Target Time Point (day)
1	Screening	-28 to -1	-28 to -1
2	Day 0	0	0
3	Day 1	Day 1 pre-dose	Day 1 pre-dose
3	Day 1	Day 1 post-dose	Day 1, 4 hrs post-dose
4	Day 2	2	2
5	Day 3	3	3
6	Day 15	15 ± 1 day	15

Data obtained during unscheduled visits will be allocated to the scheduled visit corresponding to the visit window they fall in as specified in Table 4. Data will be analyzed based on the nominal visits and nominal time points. If the data from the nominal visit or time point is missing, data from unscheduled visits for the same nominal visit or time point will be used. If multiple unscheduled assessments fall in the same visit window, the latest assessment will be selected for analysis.

If there are multiple unscheduled visits within the interval of 15 ± 1 day the latest unscheduled visit within this window will be used. If there are multiple unscheduled visits outside of the time interval of 15 ± 1 day, and there is no visit in the interval 15 ± 1 day, the visit closest to the interval of 15 ± 1 will be used.

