6.7.3.3 Hepatotoxicity

Any clinical significant increase in hepatic enzymes and specifically ALT or AST $>$ or $=$ 3x ULN (for healthy control subjects), or AST or ALT $>$ or $=$ to 3x the subject's baseline values, whichever is greater, requires immediate repeat test within 48 to 72 h to confirm the hepatic enzyme elevation. The event should be reported as an adverse event within the CRF if the enzyme elevation is confirmed or worsening. Potential contributors to hepatic enzyme elevation should be evaluated by the investigator. The investigator is encouraged to consult with the Medical Monitor regarding ongoing diagnostic workup.

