6.3.1 Study Day and Visit Window Definitions

Refer to Section 6.1.1 for details.

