8.4.2 Laboratory Data

Summary tables for laboratory parameters (including hematology, chemistry, and urinalysis) will be summarized for subjects in the Safety Population. Summaries for change from baseline for hematology, chemistry, and urinalysis parameters will include descriptive statistics (the number of non-missing values, mean, standard deviation, median, minimum and maximum) for values and change from baseline values for all continuous variables, and frequency counts and percentages for categorical variables, by treatment. Subjects with laboratory data outside the normal range will be listed with abnormal values flagged.

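### The required ALT/AST repeat, and any peak seen only at an unscheduled assessment, normally enters no safety summary table, and the SAP plans no worst-post-dose summary to catch it

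*SAP*

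**What the plan says.** SAP 6.1.1 sets the basis for the safety tables: "Data will be analyzed based on the nominal visits and nominal time points". Unscheduled data are substitutes. The SAP provides that "If the data from the nominal visit or time point is missing, data from unscheduled visits for the same nominal visit or time point" are used, and, for several in one window, "If multiple unscheduled assessments fall in the same visit window, the latest assessment will be selected for analysis". Day 15 has its own rule: if there are multiple unscheduled visits outside 15 ± 1 and no visit inside it, "the visit closest to the interval of 15 ± 1 will be used". SAP 6.3.1 carries all this over to safety: "Refer to Section 6.1.1 for details".

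The post-dose windows in SAP Table 4 are Day 1, Day 2, Day 3 and Day 15 ± 1.

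SAP 8.4.2 to 8.4.4 plan descriptive statistics of values and/or changes from baseline. They include no worst-post-dose, shift or threshold table. For laboratory data there is also a listing: "Subjects with laboratory data outside the normal range will be listed with abnormal values flagged".

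Protocol 6.7.3.3 says that an ALT or AST elevation meeting its threshold "requires immediate repeat test within 48 to 72 h to confirm the hepatic enzyme elevation". It then says: "The event should be reported as an adverse event within the CRF if the enzyme elevation is confirmed or worsening".

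**The concern.** The schedule has only two post-dose laboratory draws, Day 3 and Day 15 ± 1. The repeat in protocol 6.7.3.3 exists to show whether an enzyme rise persists or worsens, yet it tends to fall on a day that no window covers. If the repeat is the highest value, the maximum and the largest change in the laboratory table are too small. An ECG or vital-sign reading taken off schedule for a clinical reason faces the same rule.

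The Day 15 fallback creates a second problem: a value taken well before Day 15 can be summarised under that label.

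Safety and tolerability in moderate hepatic impairment is the secondary objective. With eight subjects per group, one subject is 1/8 = 12.5% of the group, and the minimum and maximum carry much of what a descriptive table can tell.

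**Working it through.** The plan states no figure on this point, so there is none to reproduce. The check maps the required repeat onto the windows and then follows one subject through the tables.

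**Inputs.** Post-dose windows are Day 1, 2, 3 and 14-16 (SAP Table 4). The last pre-dose draw is on Day 1, and post-dose draws are on Day 3 and Day 15 ± 1 (protocol Appendix 1; SAP Table 1). The repeat lag is 48 to 72 h (protocol 6.7.3.3), taken as 2 to 3 days from the draw.

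**Formula.** Repeat day = trigger day + 2 or + 3.

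| Trigger draw | Repeat day | Window in Table 4 |
|---|---|---|
| Day 1 pre-dose | 3 or 4 | Day 3 (the nominal draw is used) or none |
| Day 3 | 5 or 6 | none |
| Day 14 | 16 or 17 | Day 15 window, but the nominal value already exists; or none |
| Day 15 | 17 or 18 | none |
| Day 16 | 18 or 19 | none |

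The protocol does not say whether the 48 to 72 h runs from the draw or from receipt of the result. For a Day 3 trigger this does not matter unless the result takes more than 13 − 6 = 7 days, because every day up to Day 13 is uncovered.

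**When the repeat does reach a table.** It must replace a missing nominal value. The example that matters is a Day 5-6 repeat when no visit falls in 15 ± 1. If there are multiple out-of-window visits, the closest is summarised as Day 15 with no limit on distance. A Day 5 or 6 value would then stand 14 − 5 = 9 or 14 − 6 = 8 days before the window opens. The SAP does not say what happens to a single out-of-window visit.

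**Two related gaps.** An unscheduled pre-dose value can enter as baseline, because SAP 8.4 takes the last evaluation before dosing. An unscheduled laboratory or ECG value on Day 2 falls in a window with no scheduled assessment of that type, and the SAP does not say whether it is summarised.

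**Illustration (all values assumed).** A subject with hepatic impairment has baseline ALT 40, Day 3 value 130, repeat on Day 5 of 240 and Day 15 value 45.
- Trigger: 3 × 40 = 120 and 130 > 120, so the repeat is required.
- Largest change in the by-visit tables: 130 − 40 = 90.
- Largest change observed: 240 − 40 = 200.
- Shortfall: 200 − 90 = 110. The value 240 appears in no laboratory summary.

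If the repeat is at or below the triggering value, the shortfall is zero.

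**The case against.** The strongest reply is that nothing is lost from the report. SAP 8.1 lists CRF data, protocol 9.7 puts all safety data in by-subject listings, and SAP 8.4.3 and 8.4.4 list vital signs and ECGs. With about 16 subjects, each value can be read. Protocol 6.5, 6.7 and 6.7.3.3 turn clinically significant laboratory and ECG changes, and confirmed enzyme rises, into adverse events, and SAP 8.4.1 tabulates treatment-emergent events by group. The subject in the illustration would be counted there. All of this stands. It limits the point but does not remove it, because an incidence count by preferred term does not show how large a change was.

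Several stronger readings are tempting, and the documents do not support them:
- A reader might infer that required repeats also drop out of the ECG and vital-sign tables. Only the ALT/AST repeat is required. Protocol 6.5 and 6.7 leave ECG and other laboratory repeats to the investigator, and no on-study vital-sign repeat is required.
- A reader might infer that peaks in general disappear. The scheduled value that triggers a repeat stays in the table and its maximum; only a peak seen solely off schedule is missing.
- A reader might infer that choosing the latest value favours recovered results. That is plausible but unsourced, and the rule applies only when the nominal value is missing and several unscheduled values share a window.
- A reader might infer that normal-range flags are of little use because a Child-Pugh score of 7-9 comes mainly from laboratory items. It need not: ascites on two medications scores 3, and 1 for each of the other four items gives 3 + 4 = 7. ALT and AST are not in the score.

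The table shells are in a separate document that was not available, so a worst-value display there cannot be ruled out. The SAP text does not call for one.

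**Conclusion.** The point holds in a limited form. Under SAP 6.1.1 and Table 4 the ALT/AST repeat normally enters no laboratory summary, and neither does any laboratory, ECG or vital-sign peak seen only at an unscheduled assessment. No planned summary offsets this. The Day 15 fallback can also relabel a distant value.

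The size depends on the data. It is zero when the peak falls on a scheduled visit; otherwise it is the gap between the unscheduled and scheduled peaks (110 in the assumed example). The conclusion rests on the SAP text as written and on counting the repeat lag from the draw or from a result available within 7 days.

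The consequence is confined to descriptive safety tables for a secondary objective, with no hypothesis testing. PK and PD results are unaffected. This is a low-cost improvement to reporting, not a flaw that threatens the study's conclusions.

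**What to change.** Keep the by-visit tables and the rule that takes the latest value. Replacing latest with worst inside those tables would pull visit means away from typical values, so it is not recommended.

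- **SAP 8.4.2 to 8.4.4:** add a worst-post-dose summary by hepatic function group, with change from baseline, using every scheduled and unscheduled post-dose value. Limit it to parameters with a clear adverse direction: maximum ALT, AST, bilirubin, creatinine and QTcB; minimum glucose and systolic blood pressure. Show the number of assessments behind each summary.
- **SAP 6.1.1:** state that values outside every Table 4 window feed this summary and are not relabelled as Day 15.

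The cost is SAP wording and a few extra table rows, with no new data. The summaries may look slightly less favourable. A maximum also tends to rise with the number of samples, so a group with more repeats can look worse for that reason alone; the assessment counts let the reader judge this.
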